Because of its inverse relationship to the heart rate, the measured QT interval is routinely corrected by several formulae to a less heart rate-dependent value, which is known as the QTc interval. Fridericia's correction method (QTcF)³ is considered the more accurate general method for heart rate correction.⁴ In certain cases, individual QT correction based on QT-RR relationship is a preferred method.⁵

Substudy Design Rationale

Patients with COVID-19 included in study APL-D-003-20 allows assessment in a Phase 3 clinical trial setting similar to that for which therapeutic use of plitidepsin is being evaluated. This substudy will be conducted at some of the sites participating in study APL-D-003-20.

Although the daily variability in QTc interval in these patients' setting has not been well described, it may be even larger because enrolled patients are likely to have advanced age or concomitant medical problems.⁶ For this reason, an intrapatient standard deviation of 30 milliseconds is assumed. To reduce intrapatient variability due to measurement error, it has been recommended that the baseline QTc be rigorously investigated and be expressed as the mean of multiple ECG assessments.⁷ For this purpose, 2 sets of triplicate ECG tracings recorded before plitidepsin administration will be considered baseline assessments: 1 set before and 1 set after prophylactic antiemetic medication administration.

Electrocardiogram assessments will be performed by means of continuous 12-lead ECG automated digital collection. All digital ECG continuous recordings will be sent to a third-party central ECG laboratory for measurement of intervals, diagnostics of abnormalities and review of ECG waveform morphology review. This will prevent the potential introduction of bias during the analysis of ECG recordings.

Samples for whole blood plitidepsin concentration measurement will be collected matching the clock times of ECG measurements, and are aimed at conducting a concentration QTc analysis.

OBJECTIVES

Based on the aforementioned scientific background, the primary objective of the present substudy is to assess the potential effects of plitidepsin at a therapeutic dose on the duration of the QTc interval, measured by continuous 12-lead ECG automated monitoring, in patients with COVID-19.

Secondary objectives are:

- To characterise the plitidepsin concentration/QTc relationship.
- To explore waveform morphology-related ECG parameters

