For the triplicate ECGs collected at each timepoint, the average of the 3 measurements for each ECG parameter will be considered for all listing and statistical analyses described below.

Investigators are not expected to evaluate or otherwise assess the ECGs unless alerted by the central ECG laboratory to the possibility of a clinically relevant reading.

QT Correction Methods

The QT will be corrected for heart rate using the following methods:

- QTcF³
- Estimation of the exponent at an individual level (QTcI)⁹

The most appropriate method, based on the lack of statistical significance of the slope between QTc and heart rate, will be used for the concentration-QTc analysis.

Endpoint definition

In principle, for each patient and each postdose timepoint on Days 1 to 3, baseline QTc intervals will be the mean of the predose 1 and predose 2 QTc values for that patient on Day 1.

If the mean predose 2 QTc value of all evaluable patients is ≥ 10 msec longer than of the mean predose 1 QTc value, an effect of prophylactic medication on QTc cannot be ruled out; therefore, individual predose 2 QTc values will be considered as the baseline values.

The change from baseline (Δ QTc) will be calculated using the corresponding baseline QTc values. Specifically:

- Δ QTc at time t: Difference in QTc between scheduled timepoint t and baseline.

The primary endpoint will be Δ QTc at each scheduled timepoint.

STATISTICAL METHODS

Sample Size

Assuming that the intrasubject standard deviation for change from baseline in QTc (Δ QTc) is 30 msec and that the true difference between means is 5 msec, a sample size of at least 25 evaluable patients in more than 80% of the scheduled ECG timepoints t is planned to have 80% power to show that the upper limit of the 2-sided 90% confidence interval (CI; 1-sided upper 95% CI) for mean Δ QTc at each ECG timepoint t is < 20 msec.

Primary Analysis

“By Timepoint” Analysis

The primary objective of this QT evaluation study is to measure the potential effect of plitidepsin on QTc. The primary comparison of interest is Δ QTc at each ECG timepoint t. A noninferiority criterion of 20 msec will be used to establish that postbaseline QTc is noninferior to baseline.

An analysis of variance model (ANOVA) with mixed effects will be fitted, with Δ QTc data as the dependent variable and ECG timepoint t as the fixed effects, and patient as random effect.

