Using the estimated least square means (LSM) and intrapatient standard deviation obtained from this model, a 2-sided 90% CI will be calculated for each LSM Δ QTc. Noninferiority will be concluded if the upper bound of the 1-sided 95% CI falls below 20 msec at each ECG timepoint.

Mean QTc and corresponding changes from baseline (Δ QTc) will be listed and summarised descriptively by ECG timepoint. Plots of mean Δ QTc *versus* ECG timepoint will be prepared.

Categorical Analysis

Categorical (or outlier) reference limits will be defined in terms of change from baseline values or as absolute values, according to the ICH E14 guidance.

The incidence counts and percentage of patients with $\Delta QTc \leq 30$ msec, ΔQTc 30 to 60 msec and $\Delta QTc > 60$ msec will be tabulated for each ECG timepoint t and described for age and gender.

The incidence counts and percentage of patients with any new postbaseline QTc values > 450 msec, > 480 msec, and > 500 msec will be tabulated for each ECG timepoint t, and described for age and gender. Patients with new QT and QTc values > 500 msec will be listed.

Secondary Analyses

C- ΔQTc analysis

Exploratory Analysis

Before the model selection for the C- ΔQTc analysis, a potential delay of the ΔQTc effect relative to plasma concentrations (hysteresis) will be graphically and statistically assessed, as proposed by Darpo et al.¹⁰ Plots of the time course of mean plasma concentrations and mean ΔQTc will be overlaid, to allow detection of delay in the time to QTc peak relative to plasma concentrations. In addition, study data will be analysed to check whether any of the following 3 statistical criteria are met to conclude the presence of hysteresis:

1. Largest mean ΔQTc exceeding 5 msec at ≥ 3 timepoints
2. Time difference between U_{max} (the time of the largest mean ΔQTc) and T_{max} of plitidepsin exceeding 1 hour, and
3. One-sided 1-sample Wilcoxon test for the difference between ΔQTc at T_{max} and at U_{max} formally significant at the 1% level

If the presence of hysteresis is concluded, the primary analysis of the C- ΔQTc will be based on an effect compartment (“indirect”) model. However, if only some of the 3 criteria (not all) are met, the indirect model will be assessed and compared with a direct effect (“direct”) model and, consequently, the model that provides the best description of the available data will be used for the primary model based analysis of the C- ΔQTc .

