To enable an adequate comparison of the model fit between the direct and the indirect model, the model based predicted total plasma concentrations at central compartment (direct model) and at the effect compartment (indirect model) will be used.

Main Analysis

The relationship between total plasma concentration and ΔQTc will be assessed using a linear mixed effects (LME) model, as proposed by Garnett et al.¹¹ As the data available

come from a single arm study, the LME model will be characterised by the intercept (θ_1) and the slope (θ_2), and their corresponding variability (Equation 1, as below):

$$\Delta QTcF_{ij} = (\theta_1 \cdot e^{\eta_{1,i}}) + (\theta_2 \cdot e^{\eta_{2,i}}) \cdot C_{ij} + \theta_3 \cdot Day + e_{ij} \quad \text{Equation 1}$$

Where C_{ij} is the model-predicted plitidepsin total whole blood (observed) and or plasma (model-based estimated, as sensitivity analysis) concentrations (or the plitidepsin-concentrations in the effect compartment if a hysteresis is present), and $\eta_{1,i}$ and $\eta_{2,i}$ are the random effects associated with the intercept term θ_1 and the slope term θ_2 , respectively, and are assumed to be exponential, independent and normally distributed. Furthermore, e_{ij} is the random residual variability, assumed to be an additive, independent, and normally distributed random variable. In the absence of placebo data, the unstructured placebo model consisting on the fixed effect parameters accounting for treatment-specific intercept (TRT), mean QTc change from baseline at each timepoint evaluated ($TIME$), and baseline QTc, will not be included in the model. The model-based prediction of the total plasma concentrations will be based on the individual PK parameters, obtained through a maximum *a posteriori* estimation based on the individual total plasma concentration available for each subject and a population PK model of plitidepsin, previously developed.¹² Based on the fact that ECG assessments in this study will be performed on 2 occasions (Days 1 and 2), the effect of Day θ_3 will also be assessed in the models.

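### The secondary concentration-QTc model in Appendix 8 puts exponential random effects on a change from baseline that can have either sign, and drops baseline QTc for a reason that does not hold

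*Protocol*

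**What the plan says.** All references are to Protocol Appendix 8.

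- **Model (Secondary Analyses, Main Analysis).** The concentration-ΔQTc relationship "will be assessed using a linear mixed effects (LME) model". Equation 1 is ΔQTcF = θ1·exp(η1) + θ2·exp(η2)·C + θ3·Day + e. The random effects on intercept and slope "are assumed to be exponential, independent and normally distributed"; the residual is additive and normal.
- **Baseline term.** "In the absence of placebo data, the unstructured placebo model consisting on the fixed effect parameters" for treatment and time "and baseline QTc, will not be included in the model".
- **Baseline value (Endpoint definition).** Each patient's baseline "will be the mean of the predose 1 and predose 2 QTc values for that patient on Day 1", with predose 2 alone as the fallback if prophylaxis appears to lengthen QTc.
- **Status (Objectives).** "To characterise the plitidepsin concentration/QTc relationship" is a secondary objective.
- **Primary analysis.** A by-timepoint mixed ANOVA of the same ΔQTc, with patient as an ordinary random effect. "Noninferiority will be concluded if the upper bound of the 1-sided 95% CI falls below 20 msec at each ECG timepoint". For its sample size, the intrasubject SD of ΔQTc "is 30 msec and that the true difference between means is 5 msec, a sample size of at least 25 evaluable patients", at 80% power.

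No confidence limit, margin or decision rule is given for the concentration-QTc model.

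**The concern.** Multiplying by exp(η) makes individual intercepts and slopes log-normal. This has three consequences:

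- If θ1 is positive, no patient can have a negative intercept. The same holds for θ2 and the slopes.
- Spread is tied to the mean. As θ goes to zero, the between-patient SD goes to zero with it.
- The value at η = 0 is a median, not a mean.

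A change from baseline does not behave this way. All of a patient's changes are taken from one baseline measured with error, so intercepts scatter on both sides of a mean that should lie near zero. The model is also non-linear in its random effects, which contradicts its label. The primary ANOVA assumes an ordinary patient effect for the same data, and no reason is given for the difference.

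At stake is the accuracy of the predicted QTc effect at peak concentration. The substudy enrols only plitidepsin patients, so no control arm would expose a poorly fitted intercept.

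The reason given for leaving out baseline QTc also fails. Treatment and time terms may need placebo data, but a baseline covariate does not, and every patient has one.

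**Working it through.** **1. The plan's own figure.** The only number tied to a QTc limit is the sample size of the by-timepoint analysis: n = [30 × (1.645 + 0.842) / (20 − 5)]² = 24.73, rounded up to 25. It reproduces (noncentral-t power at 25 is 78.3%). Equation 1 plays no part in it.

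**2. Log-normal arithmetic.** Mean = θ·exp(ω²/2); SD = mean × √(exp(ω²) − 1).

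- θ = 1 msec, ω = 0.5: mean 1.13, SD 0.60 msec.
- θ = 1 msec with SD forced to 10 msec: ω = 1.53, and the mean becomes 3.24 msec.
- The typical value lies below the mean by 1 − exp(−ω²/2): 12% for ω = 0.5 and 39% for ω = 1.
- With additive variation of SD 10 msec, the share of patients with a negative value is 50%, 46% and 42% for means of 0, 1 and 2 msec. Equation 1 allows none of them when θ is positive.

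**3. What the shared baseline implies.** The SD of ΔQTc is 30 msec and baseline is the mean of two predose sets. Assume equal, independent errors (not stated in the protocol). Then 30² = σ²(1 + 1/2), so σ = 24.5 msec and the baseline error is 24.5/√2 = 17.3 msec. That error is common to all of a patient's changes, so intercepts scatter by about 17 msec either way before any true difference between patients. With θ1 = 1 msec, an SD of 17.3 needs ω of about 1.7 and moves the mean to about 4.2 msec.

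**4. Simulation.** There were 250 trials per scenario, with 50 patients (the substudy target) and 8 post-dose ECG times. Assumptions not in the protocol:

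- residual SD 30 msec, borrowing the protocol's SD of change;
- additive between-patient SD of 10 msec for the intercept, and 5 msec for the slope effect at peak (about 0 in the first row);
- concentrations at 1, 0.4, 0.25 and 0.08 of peak, with CV about 30%.

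Both models were fitted by maximum likelihood. Entries are the median one-sided 95% upper limit at peak in msec, with coverage of the true mean in brackets. Intercept and slope effect at peak are in msec.

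| Intercept, slope | Additive | Eq. 1, typical patient | Eq. 1, population mean |
|---|---|---|---|
| 0, 0 | 4.7 (94%) | 4.3 (94%) | 4.2 (87%) |
| 0, +5 | 10.1 (93%) | 9.2 (77%) | 10.0 (84%) |
| +5, +5 | 15.1 (93%) | 11.6 (65%) | 14.9 (86%) |
| 0, +10 | 15.1 (93%) | 14.3 (81%) | 15.3 (92%) |
| −5, +10 | 10.1 (93%) | 11.2 (92%) | 10.3 (93%) |
| 0, −5 | 0.1 (93%) | 1.1 (95%) | −0.6 (86%) |

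From the unrounded limits, the typical-patient shortfall in rows two to four is 0.9, 3.5 and 0.7 msec. In row one it is 0.3 msec with unchanged coverage. In the last two rows the limit is about 1.1 msec higher. Monte Carlo error in coverage is about 1.5 to 3 points.

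**5. Omitting baseline QTc.** Assumed: regression of ΔQTc on baseline −0.3, baseline SD 20 msec, patient SD 8 msec, residual 30 msec over 8 times, 50 patients, true mean 5 msec. The variance removed by adjustment is 0.3² × 20² = 36; what remains is 64 + 900/8 = 176.5. The expected SE is √(212.5/50) = 2.06 without baseline and √(176.5/50) = 1.88 with it. Simulated averages were 2.04 and 1.86. The estimate was 5.01 either way, so the upper limit was 8.4 msec without baseline and 8.1 with it.

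**The case against.** The strongest reply is that little depends on Equation 1. The analysis is secondary, and the noninferiority rule belongs to the by-timepoint ANOVA, which has no exponential term. Section 8 of the protocol leaves specific details to the SAP, which is not at hand and may say that the population mean is reported. On that reading the median limit stays within about 0.7 msec of the additive model. The simulated data were also drawn with additive variation, which favours the additive fit. All of this stands, and it limits the severity. It does not remove the point: the protocol itself writes out the random-effects form, and even for the population mean coverage was 84% to 87% in four of the six scenarios.

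A reader might infer four stronger things that the protocol does not support:

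- **That the model cannot fit effects near zero.** θ1 and θ2 can be zero, and with both true effects at zero typical-patient coverage was 94%. What fails is the spread between patients and the representation of patients of opposite sign.
- **That it always understates QT prolongation.** The direction depends on the signs of intercept and slope, and on which prediction is reported.
- **That the 20 msec conclusion is compromised.** That rule is not tied to this model.
- **That omitting baseline QTc flatters the result.** It widens the interval slightly.

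**Conclusion.** The point holds as a mis-specification of a secondary model. Exponential random effects suit a change that can go either way poorly, and they contradict the linear mixed effects label.

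Under the assumed SDs and concentration profile, the typical patient's upper limit at peak is about 0.7 to 3.5 msec too low when the slope is positive and the intercept zero or positive, with coverage about 65% to 81% against 93%. Elsewhere it is about unchanged or about 1 msec high. These sizes would change with other between-patient SDs, which the protocol does not give. The sign constraint and the link between spread and mean follow from the equation and need no such assumption.

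Dropping baseline QTc is poorly justified and costs some precision (SE about 2.04 against 1.86 under the stated assumptions). Severity is low to moderate.

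**What to change.** Replace Equation 1 with additive normal random effects and a centred baseline term:

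ΔQTc = (θ1 + η1) + (θ2 + η2)·C + θ3·Day + θ4·(baseline QTc − mean baseline QTc) + e

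State that the reported result is the predicted population-mean ΔQTc at peak concentration with its 2-sided 90% CI. The equation then matches its label and handles patient effects in the same way as the primary ANOVA. Limit the placebo reason to the treatment and time terms.

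The cost is one equation and a sentence in Appendix 8, repeated in the SAP, plus one more fixed parameter to estimate. No new data are needed, since baseline QTc is already collected.

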Amiodarone (Cordarone®)	Antiarrhythmic/abnormal heart rhythm	1
Anagrelide (Agrylin®, Xagrid®)	Phosphodiesterase inhibitor/thrombocythaemia	1
Arsenic trioxide (Trisenox®)	Anticancer/leukaemia	1
Astemizole (Hismanal®)	Antihistamine/allergic rhinitis	1
Azithromycin (Zithromax®)	Antibiotic/bacterial infection	1
Bepridil (Vascor®)	Antiangular/heart pain	1
Chloroquine (Aralen®)	Antimalarial/malaria infection	1
Chlorpromazine (Thorazine®)	Antipsychotic/antiemetic/schizophrenia/nausea	1
Cilostazol (Pletal®)	Phosphodiesterase inhibitor/intermittent claudication	1
Cisapride (Propulsid®)	Gastrointestinal stimulant/heartburn	1
Citalopram (Celexa®)	Antidepressant/depression	1
Clarithromycin (Biaxin®)	Antibiotic/bacterial infection	1
Cocaine	Local anaesthetic	1
Disopyramide (Norpace®)	Antiarrhythmic/abnormal heart rhythm	1
Dofetilide (Tikosyn®)	Antiarrhythmic/abnormal heart rhythm	1
Domperidone (Motilium®)	Antinausea/nausea	1
Donepezil (Aricept®)	Cholinesterase inhibitor/Dementia	1
Dronedarone (Multaq®)	Antiarrhythmic/atrial fibrillation	1
Droperidol (Inapsine®)	Sedative;antinausea/anaesthesia adjunct, nausea	1
Erythromycin (E.E.S.®)	Antibiotic; gastrointestinal stimulant/bacterial infection; increase gastrointestinal motility	1
Escitalopram (Cipralex®)	Antidepressant/depression/anxiety disorders	1
Flecainide (Tambocor®)	Antiarrhythmic/abnormal heart rhythm	1
Halofantrine (Halfan®)	Antimalarial/malaria infection	1
Haloperidol (Haldol®)	Antipsychotic/schizophrenia, agitation	1
Ibutilide (Corvert®)	Antiarrhythmic/abnormal heart rhythm	1
Levomethadyl (Orlaam®)	Opiate agonist/pain control, narcotic dependence	1
Mesoridazine (Serentil®)	Antipsychotic/schizophrenia	1

Generic Name (Brand Name)	Drug Class/Clinical Usage	Risk List
Methadone (Methadose®)	Opiate agonist/pain control, narcotic dependence	1
Moxifloxacin (Avelox®)	Antibiotic/bacterial infection	1
Ondansetron (Zofran®)	Antiemetic/nausea and vomiting	1
Pentamidine (Pentam®)	Antiinfective/pneumocystis pneumonia	1
Pimozide (Orap®)	Antipsychotic/Tourette's tics	1
Probucol (Lorelco®)	Antilipemic/hypercholesterolaemia	1
Procainamide (Procan®)	Antiarrhythmic/abnormal heart rhythm	1
Quinidine (Quinaglute®)	Antiarrhythmic/abnormal heart rhythm	1
Sevoflurane (Ulane®)	Anaesthetic, general/anaesthesia	1
Sotalol (Betapace®)	Antiarrhythmic/abnormal heart rhythm	1
Sparfloxacin (Zagam®)	Antibiotic/bacterial infection	1
Sulpiride (Dogmatil®, Dolmatil®)	Antipsychotic, atypical/schizophrenia	1
Terfenadine (Seldane®)	Antihistamine/allergic rhinitis	1
Thioridazine (Mellaril®)	Antipsychotic/schizophrenia	1
Vandetanib (Caprelsa®)	Anticancer/thyroid cancer	1

Risk Level 2: Possible risk of TdP: Substantial evidence supports the conclusion that these drugs can cause QT prolongation BUT there is insufficient evidence at this time that these drugs, when used as directed in official labelling, are associated with a risk of causing TdP.

Risk Level 3: Conditional risk of TdP: Substantial evidence supports the conclusion that these drugs are associated with a risk of TdP BUT only under certain conditions (e.g., excessive dose, hypokalaemia, congenital long QT or by causing a drug-drug interaction that results in excessive QT interval prolongation).

Risk Levels 1 to 4: Drugs to Avoid in Congenital Long QT: Substantial evidence supports the conclusion that these drugs pose a risk of TdP for patients with congenital long QT. Drugs on this list include those in the above 3 risk categories 1, 2, and 3, and other drugs, 4, that do not prolong the QT interval per se but have a theoretical risk of causing arrhythmia that is based on their known stimulant actions on the heart.

Generic Name (Brand Name)	Drug Class/Clinical Usage	Risk List
Albuterol/salbutamol (Proventil®, Ventolin)	Bronchodilator/asthma	4
Alfuzosin (Uroxatral®)	Alpha1-blocker/benign prostatic hyperplasia	2
Amantadine (Symmetrel®)	antiviral/anti-infective/Parkinson's disease	3
Amphetamine (Adderal-XR®, Dexedrine®)	CNS stimulant/ADHD	4
Amiodarone (Cordarone®)	Antiarrhythmic/abnormal heart rhythm	1
Amisulpride (Solian® and others)	Antipsychotic, atypical/psychosis	3
Amitriptyline (Elavil®)	Tricyclic antidepressant/depression	3
Amoxapine (Asendin®, Amokisan®)	Tetracyclic antidepressant/depression	3
Anagrelide (Agrylin®, Xagrid®)	Phosphodiesterase inhibitor/thrombocythaemia	1
Apomorphine (Apokyn®, Ixense®)	Dopamine agonist/Parkinson's disease	2

Generic Name (Brand Name)	Drug Class/Clinical Usage	Risk List
Aripiprazole (Abilify®, Aripiprex®)	Antipsychotic/psychosis, adjunct for depression	2
Arsenic trioxide (Trisenox®)	Anticancer/leukaemia	1
Arformoterol (Brovana®)	Bronchodilator/chronic obs. lung disease	4
Astemizole (Hismanal®)	Antihistamine/allergic rhinitis	1
Atazanavir (Reyataz®)	Protease inhibitor/HIV	2
Atomoxetine (Strattera®)	Norepinephrine reuptake inhibitor/ADHD	4
Azithromycin (Zithromax®)	Antibiotic/bacterial infection	1
Bedaquiline (Sirturo®)	Anti-infective/drug-resistant tuberculosis	2
Bepridil (Vascor®)	Antianginal/heart pain	1
Bortezomib (Velcade®, Bortecad®)	Proteasome inhibitor/multiple myeloma,lymphoma	2
Bosutinib (Bosulif®)	Tyrosine kinase inhibitor/leukaemia	2
Chloral hydrate (Noctec®)	Sedative/sedation/insomnia	3
Chloroquine (Aralen®)	Antimalarial/malaria infection	1
Chlorpromazine (Thorazine®)	Antipsychotic/antiemetic/schizophrenia/nausea	1
Cilostazol (Pletal®)	Phosphodiesterase inhibitor/intermittent claudication	1
Ciprofloxacin (Cipro®)	Antibiotic/bacterial infection	3
Cisapride (Propulsid®)	Gastrointestinal stimulant/heartburn	1
Citalopram (Celexa®)	Antidepressant/depression	1
Clarithromycin (Biaxin®)	Antibiotic/bacterial infection	1
Clomipramine (Anafranil®)	Tricyclic antidepressant/depression	3
Clozapine (Clozaril®)	Antipsychotic/schizophrenia	2
Cocaine	Local anaesthetic	1
Crizotinib (Xalkori®)	Kinase inhibitor/anticancer	2
Dabrafenib (Tafinlar®)	Anticancer/melanoma	2
Dasatinib (Sprycel®)	Tyrosine kinase inhibitor/leukaemia	2
Desipramine (Pertofrane®)	Tricyclic antidepressant/depression	3
Dexmedetomidine (Precedex®, Dexdor®)	Sedative/sedation	2
Dexmethylphenidate (Focalin®)	CNS stimulant/ADHD	4
Dextroamphetamine (Dexedrine®)	CNS stimulant/ADHD	4
Dihydroartemis.+piperaquine (Eurartesim®)	Antimalarial/malaria	2
Diphenhydramine (Benadryl®)	Antihistamine/allergic rhinitis, insomnia	3
Disopyramide (Norpace®)	Antiarrhythmic/abnormal heart rhythm	1
Dobutamine (Dobutrex®)	Inotrope/heart failure, shock	4
Dopamine (Intropine®)	Inotrope/heart failure, shock	4
Dofetilide (Tikosyn®)	Antiarrhythmic/abnormal heart rhythm	1
Dolasetron (Anzemet®)	Antinausea/nausea, vomiting	2
Domperidone (Motilium®)	Antinausea/nausea	1

Generic Name (Brand Name)	Drug Class/Clinical Usage	Risk List
Donepezil (Aricept®)	Cholinesterase inhibitor/dementia	1
Doxepin (Sinequan®)	Tricyclic antidepressant/depression	3
Dronedarone (Multaq®)	Antiarrhythmic/atrial fibrillation	1
Droperidol (Inapsine®)	Sedative;antinausea/anaesthesia adjunct, nausea	1
Ephedrine (Rynatuss®, Broncholate®)	Bronchodilator, decongestant/allergies, asthma	4
Epinphrine (Primatene®, Bronkaid®)	Vasoconstrictor/Anaphilaxis, allergic reactions	4
Eribulin (Halaven®)	Anticancer/metastatic breast neoplasias	2
Erythromycin (E.E.S.®)	Antibiotic; gastrointestinal stimulant/bacterial infection; increase gastrointestinal motility	1
Escitalopram (Cipralex®)	Antidepressant/depression/anxiety disorders	1
Famotidine (Pepcid®)	H2-receptor antagonist/peptic ulcer/gastroesophageal reflux disease	2
Felbamate (Felbatrol®)	Anticonvulsant/seizure	2
Fenfluramine (Pondimin®, Ponderax®)	Appetite suppressant/Dieting, weight loss	4
Fingolimod (Gilenya®)	Immunosuppressant/multiple sclerosis	2
Flecainide (Tambocor®)	Antiarrhythmic/abnormal heart rhythm	1
Fluconazole (Diflucan®)	Antifungal/fungal infection	3
Fluoxetine (Sarafem®)	Antidepressant/depression	3
Formoterol (Foradil, Foralide)	Bronchodilator /Asthma	4
Foscarnet (Foscavir®)	Antiviral/HIV infection	2
Fosphenytoin (Cerebyx®)	Anticonvulsant/seizure	2
Furosemide/Frisemide (Lasix®, Fusid®)	Diuretic/increase urine & salt loss	3
Galantamine (Reminyl®)	Cholinesterase inhibitor/dementia, Alzheimer's	3
Gatifloxacin (Tequin®)	Antibiotic/bacterial infection	2
Gemifloxacin (Factive®)	Antibiotic/bacterial infection	2
Granisetron (Kytril®)	Antinausea/nausea and vomiting	2
Halofantrine (Halfan®)	Antimalarial/malaria infection	1
Haloperidol (Haldol®)	Antipsychotic/schizophrenia, agitation	1
Hydrochlorothiazide (Apo-Hydro®)	Diuretic/increase urine & salt loss	3
Ibutilide (Corvert®)	Antiarrhythmic/abnormal heart rhythm	1
Iloperidone (Fanapt®)	Antipsychotic, atypical/schizophrenia	2
Imipramine (Norfranil®)	Tricyclic antidepressant/depression	3
Indapamide (Lozol®)	Diuretic/stimulate urine & salt loss	3
Isoproterenol (Medihaler-Iso®, Isuprel®)	Bronchodilator/allergic reaction	4
Isradipine (Dynacirc®)	Antihypertensive/high blood pressure	2
Itraconazole (Sporanox®)	Antifungal/fungal infection	3
Ivabradine (Procoralan®, Coralan®)	Antianginal/angina pectoris (heart pain)	3
Ketoconazole (Nizoral®)	Antifungal/fungal infection	3

Generic Name (Brand Name)	Drug Class/Clinical Usage	Risk List
Lapatinib (Tykerb®)	Anticancer/breast cancer, metastatic	2
Levalbuterol (Xopenex®, Levolin®)	Bronchodilator/Asthma	4
Levofloxacin (Levaquin®)	Antibiotic/bacterial infection	2
Levomethadol (Orlaam®)	Opiate agonist/pain control, narcotic dependence	1
Lisdexamfetamine (Vyvanse®)	CNS stimulant/ADHD	4
Lithium (Lithobid®)	Antimania/bipolar disorder	2
Mesoridazine (Serentil®)	Antipsychotic/schizophrenia	1
Metaproterenol (Metaprel®, Alupent®)	Bronchodilator/asthma	4
Methadone (Methadose®)	Opiate agonist/pain control, narcotic dependence	1
Methamphetamine (Desoxyn®, Pervitin®)	CNS stimulant/Obesity, ADHD	4
Methylphenidate (Ritalin®, Concerta®)	CNS stimulant/ADHD	4
Metronidazole (Flagyl®)	Antibiotic/trichomoniasis, amebiasis, bacterial infection	3
Midodrine (ProAmatine®, Amatine®)	Vasoconstrictor/Low blood pressure, fainting	4
Mifepristone (Korlym®, Mifeprex®)	Progesterone antagonist/pregnancy termination	2
Mirabegron (Myrbetriq®)	Beta3 adrenergic antagonist/overactive bladder	2
Mirtazapine (Remeron®)	Antidepressant/depression	2
Moexipril/HCTZ (Uniretic®)	Antihypertensive/high blood pressure	2
Moxifloxacin (Avelox®)	Antibiotic/bacterial infection	1
Nelfinavir (Viracept®)	Antiviral/HIV/AIDS	3
Nicardipine (Cardene®)	Antihypertensive/high blood pressure	2
Nilotinib (Tasigna®)	Anticancer/leukaemia	2
Norepinephrine (Levophed ®)	Vasoconstrictor/Shock, low blood pressure	4
Norfloxacin (Noroxin®, Ambigram®)	Antibiotic/bacterial infection	2
Nortriptyline (Pamelor®)	Tricyclic Antidepressant/depression	3
Ofloxacin (Floxin®)	Antibiotic/bacterial infection	2
Olanzapine (Zyprexa®)	Antipsychotic, atypical/schizophrenia, bipolar	2
Ondansetron (Zofran®)	Antiemetic/nausea and vomiting	1
Oxytocin (Pitocin®)	Oxytocic/labour stimulation	2
Paliperidone (Invega®)	Antipsychotic, atypical/schizophrenia	2
Paroxetine (Paxil®)	Antidepressant/depression	3
Pasireotide (Signifor®)	Somatostatin analogue/Cushing's Disease	2
Pazopanib (Votrient®)	Tyrosine kinase inhibitor/anticancer	2
Pentamidine (Pentam®)	Anti-infective/pneumocystis pneumonia	1
Perflutren lipid microspheres (Definity®)	Imaging contrast agent/echocardiography	2
Phentermine (Adipex P®, Adiphene®)	Appetite suppressant/Dieting, weight loss	4
Phenylephrine (Neosynephrine®)	Vasoconstrictor/Low blood pressure, allergies	4
Phenylpropanolamine (Acutrim, Dexatrim®)	Appetite suppressant/Obesity	4

Generic Name (Brand Name)	Drug Class/Clinical Usage	Risk List
Pimozide (Orap®)	Antipsychotic/Tourette's tics	1
Pipamperone (Dipiperon®, Propitan®)	Antipsychotic/schizophrenia	2
Posaconazole (Noxafil®, Posamol®)	Antifungal/fungal infection	3
Probucol (Lorelco®)	Antilipemic/hypercholesterolemia	1
Procainamide (Procan®)	Antiarrhythmic/abnormal heart rhythm	1
Promethazine (Phenergan®)	Antipsychotic-antiemetic/nausea	2
Protriptyline (Vivactil®)	Tricyclic antidepressant/depression	3
Pseudoephedrine (PediaCare®, Sudafed®)	Decongestant/allergies, sinusitis, asthma	4
Quetiapine (Seroquel®)	Antipsychotic/schizophrenia	2
Quinidine (Quinaglute®)	Antiarrhythmic/abnormal heart rhythm	1
Quinine sulfate (Qualaquin®)	Antimalarial/malaria or leg cramps	3
Ranolazine (Ranexa®)	Antianginal/chronic angina	2
Rilpivirine (Edurant®, Complera®)	Antiviral/HIV/AIDS	2
Risperidone (Risperdal®)	Antipsychotic/schizophrenia	2
Ritodrine (Yutopar®)	Muscle relaxant/Prevent premature labour	4
Ritonavir (Norvir®)	Protease inhibitor/HIV	3
Roxithromycin* (Rulide®)	Antibiotic/bacterial infection	2
Saquinavir (Invirase®)	Antiviral/HIV/AIDS	2
Salmeterol (Serevent®, Advair®)	Bronchodilator/Asthma, COPD	4
Sertindole (Serolect®)	Antipsychotic, atypical/anxiety, schizophrenia	2
Sertraline (Zoloft®)	Antidepressant/depression	3
Sevoflurane (Ulane®)	Anaesthetic, general/anaesthesia	1
Sibutramine (Meridia®)	Appetite suppressant/Dieting, weight loss	4
Solifenacin (VESIcare®)	Muscarinic receptor antagonist/overactive bladder	3
Sorafenib (Nexavar®)	Tyrosine kinase inhibitor/anticancer	2
Sotalol (Betapace®)	Antiarrhythmic/abnormal heart rhythm	1
Sparfloxacin (Zagam®)	Antibiotic/bacterial infection	1
Sulpiride (Dogmatil®, Dolmatil®)	Antipsychotic, atypical/schizophrenia	1
Sunitinib (Sutent®)	Anticancer/RCC, GIST	2
Tacrolimus (Prograf®)	Immunosuppressant/immune suppression	2
Tamoxifen (Nolvadex®)	Anticancer/breast cancer	2
Telaprevir (Incivek®, Incivo®)	Antiviral/hepatitis C	3
Telavancin (Vibativ®)	Antibiotic/bacterial infection	2
Telithromycin (Ketek®)	Antibiotic/bacterial infection	2
Terbutaline (Brethine®, Bricanyl®)	Bronchodilator/Asthma, premature labour	4
Terfenadine (Seldane®)	Antihistamine/allergic rhinitis	1
Tetrabenazine (Nitoman®, Xenazine®)	Monoamine transporter inhibitor/chorea	2
Thioridazine (Mellaril®)	Antipsychotic/schizophrenia	1

Generic Name (Brand Name)	Drug Class/Clinical Usage	Risk List
Tizanidine (Zanaflex®)	Muscle relaxant/spasticity	2
Tolterodine (Detrol®, Detrusitol®)	Muscle relaxant/bladder spasm	2
Toremifene (Fareston®)	Oestrogen agonist/antagonist/anticancer	2
Trazodone (Desyrel®)	Antidepressant/depression, insomnia	3
Trimethoprim-Sulfa (Septra® or Bactrim®)	Antibiotic/bacterial infection	3
Trimipramine (Surmontil®)	Tricyclic antidepressant/depression	3
Vandetanib (Caprelsa®)	Anticancer/thyroid cancer	1
Vardenafil (Levitra®)	Phosphodiesterase inhibitor/vasodilator	2
Vemurafenib (Zelboraf®)	Kinase inhibitor/anticancer	2
Venlafaxine (Effexor®)	Antidepressant/depression	2
Voriconazole (Vfend®)	Antifungal/fungal infection	3
Vorinostat (Zolinza®)	Anticancer/lymphoma	2
Ziprasidone (Geodon®)	Antipsychotic/schizophrenia	2

A note about brand names: drugs are listed with up to two common brand names. There are many more brand names for some of the common drugs, such as pseudoephedrine and erythromycin.

